6.3 Patient Disposition

The number of patients screened (i.e., signed informed consent) will be presented. The number and percentage of patients randomized, patient population (ITT, Safety Populations, and PK Population), and treatment status (completed, discontinued / withdrew) will be summarized by treatment group and overall. Reasons for discontinuation/withdrawal will be presented.

6.4 Protocol Deviations

An incident involving noncompliance with the protocol, but one which typically does not have significant effects on the patient's rights, safety, or welfare, or the integrity of the resultant data will be considered a protocol deviation. An incident involving noncompliance with the protocol which may affect the patient's rights, safety, or welfare, or the integrity of the resultant data will be known as a protocol violation. In particular, any serious deviation that affects the collection of data for the primary endpoint will be considered a protocol violation. In general, protocol exemptions will not be granted.

Examples of potential protocol violations may include violation of important admission (inclusion/exclusion) criteria, occurrence of a treatment dispensing error, treatment noncompliance or substantial use of a prohibited medication during the study. Reported protocol deviations and patient data will be examined prior to database lock to determine if conditions set forth in the study protocol have been violated and a more comprehensive list will be constructed at that time. The complete list of major protocol deviations will not be summarized; however, a list of major protocol deviation will be presented.

6.5 Demographic and Baseline Characteristics

Demographic and baseline characteristics (e.g., age [years], race, ethnicity, weight [kg], height [cm], BMI [kg/m²], genotype, country, age at onset of Hunter syndrome symptoms, age of Hunter syndrome diagnosis, family history of Hunter syndrome) will be summarized by treatment group and overall. The genotype will be summarized into the following categories:

- Complex rearrangement
- Frameshift
- Missense
- Nonsense
- Splice site mutation

$BMI = \text{weight (kg)} / (\text{height (m)})^2$. $\text{Age} = (\text{date of event} - \text{birth date} + 1) / 365.25$.

Date of event is defined as randomization date for the pivotal study patients, and date of eligibility (enrollment date) for the substudy patients. If only the event day is missing, the day

will be assigned as 15. If both the day and month are missing, they will be assigned as July 1st. One decimal will be shown for BMI and age.

Medical history will be coded by the Medical Dictionary for Regulatory Activities (MedDRA) version 16.1 or higher and surgical history will be coded by the Shire Medical Monitor. This data will be summarized by treatment group.

6.6 Treatment Compliance and Extent of Exposure

The number of IT injections received overall and by lumbar puncture, average dose, the duration of idursulfase-IT treatment and IT administration duration will be summarized descriptively in the idursulfase-IT arm.

The duration of idursulfase-IT treatment, summarized in months, is defined as the time from first to last IT administration during the study.

The duration for each idursulfase-IT administration (in minutes) is calculated by subtracting the administration start time from the administration end time. The actual average duration of idursulfase-IT administration (in minutes) will be calculated as an average value of the idursulfase-IT administrations across all available administrations for the same patient.

Treatment compliance will be summarized in terms of the percent of scheduled doses received in the idursulfase-IT arm. The percent of scheduled doses received for each patient is defined as: $[(\text{Number of Complete IT injections Received}) \div (\text{Expected Number of IT injections at EOS})] * 100$.

6.7 Analysis of Efficacy

All efficacy analyses described below refer to the pivotal study; all efficacy data from patients treated in the separate substudy will be listed, including measurements from the BSID-III, VABS-II, PD data and DAS-II if available. All change from baseline endpoints are calculated as the value of the corresponding visit minus the value at baseline.

6.7.1 Primary Analysis

For the pivotal study, the primary efficacy endpoint is the change from study baseline (Screening Visit) to Visit Week 52 in the General Conceptual Ability (GCA) score as measured by the DAS-II. The primary analysis will compare the treatment groups using a linear mixed model repeated measures (MMRM) analysis (Malinckrodt et al. 2008; Siddiqui et al. 2009). The repeated measures are the change from baseline GCA score obtained at the scheduled Visit Weeks 16, 28, 40, and 52, respectively. The model will include fixed categorical effects for treatment, visit week, treatment by visit week interaction, baseline GCA classification factor (either ≤ 70 or > 70), baseline age group (either < 6 years or ≥ 6 years), treatment by baseline GCA classification factor interaction, treatment by baseline age group interaction, interaction between baseline GCA classification factor and baseline age group, genotype, and the baseline GCA score as a continuous covariate. Visit week is defined as nominal visits, unless specified otherwise.

SAS Proc Mixed with restricted maximum likelihood estimation (REML) and an unstructured within-patient covariance structure will be used. If this model fails to converge, a first order autoregressive (AR(1)) covariance structure will be used for the primary analysis. Due to small sample size of ITT Population with baseline age ≥ 6 years, MMRM model may fail to converge when low count of subjects with baseline age ≥ 6 years exists in either treatment group. If this model fails to converge, the treatment by baseline age group interaction and /or interaction between baseline GCA classification factor and baseline age group will be removed from the model. The Kenward-Roger approximation will be used to estimate denominator degrees of freedom for tests of fixed effects. The assumptions of the model, including normality, will be evaluated using residual and other diagnostic plots of model fit.

From this model, least squares means, standard errors, treatment differences in least squares means, and 95% confidence intervals will be estimated for each time point. Primary inference will be based on the treatment comparison of least squares means at Visit Week 52 from this model, and a p-value will be presented for this time point only. The null hypothesis is that the mean difference in the primary endpoint between the two treatment groups is zero, versus the alternative hypothesis that this difference is not zero. The hypotheses can be expressed as follows:

$$H_0: \mu_{IT} - \mu_{control} = 0 \text{ versus } H_1: \mu_{IT} - \mu_{control} \neq 0$$

Where μ_{IT} refers to the mean change from baseline to Visit Week 52 in GCA score in the idursulfase-IT treated group and $\mu_{control}$ refers to the mean change from baseline to Visit Week 52 in GCA score in the No IT treatment group. The test will be performed using the final, MMRM model-based t-test with a two-sided significance level of 5%. Estimated least squares means for change from baseline and the observed absolute values (\pm SE) by treatment group will be plotted over time.

The sample SAS code is presented in [appendix 9.2.1](#).

As a sensitivity analysis for the primary analysis using ITT population, MMRM model in the same manner as described above will be conducted for a subset of ITT population, which includes all ITT subjects excluding subjects enrolled from the observational study HGT-HIT-090 who experienced a decrease in GCA score of ≥ 10 points over 12 months in study HGT-HIT-090 prior to being enrolled in study HGT-HIT-094 and a GCA score at HGT-HIT-094 Screening >85 points.

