6.7.2 Key Secondary Analysis

The key secondary efficacy endpoint is the change from study baseline (Screening Visit) to Visit Week 52 in the Adaptive Behavior Composite (ABC) score as measured by the VABS-II. The key secondary analysis will compare the treatment groups using a linear mixed model repeated measures (MMRM) analysis. The repeated measures are the change from baseline ABC scores obtained at the scheduled Visit Weeks 16, 28, 40, and 52, respectively. The model will include fixed categorical effects for treatment, visit week, treatment by visit week interaction, baseline GCA classification factor (either ≤ 70 or >70), baseline age group (either <6 years or ≥ 6 years),

treatment by baseline GCA classification factor interaction, treatment by baseline age group interaction, interaction between baseline GCA classification factor and baseline age group, genotype, and the baseline ABC score as a continuous covariate.

SAS Proc Mixed with restricted maximum likelihood estimation (REML) and an unstructured within-patient covariance structure will be used. If this model fails to converge, a first order autoregressive (AR(1)) covariance structure will be used instead. The Kenward-Roger approximation will be used to estimate denominator degrees of freedom for tests of fixed effects. The assumptions of the model, including normality, will be evaluated using residual and other diagnostic plots of model fit.

From this model, least squares means, standard errors, treatment differences in least squares means, and 95% confidence intervals will be estimated for each time point. The significance test will be based on the treatment comparison of least squares means at Visit Week 52 from this model, and a p-value will be presented for this time point only. Estimated least squares means for change from baseline and the observed absolute values (\pm SE) by treatment group will be plotted over time.

The sample SAS code is presented in [appendix 9.2.2](#).

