6.7.3 Other Secondary Analyses

The following secondary efficacy endpoints will be analyzed using a MMRM analysis in the same manner as described above for the key secondary endpoint with the continuous covariate corresponding to the baseline score for each measure:

- The change from baseline to Visit Weeks 16, 28, 40, and 52 in standard scores in cluster areas of the DAS-II: Verbal, Nonverbal, Spatial, and Special Nonverbal Composite (SNC)
- The change from baseline to Visit Weeks 16, 28, 40, and 52 in the standard scores of the VABS-II: Communication, Daily Living Skills, Socialization, and Motor Skills
- The change from baseline to Visit Weeks 16, 28, 40, and 52 in the T scores for the six core subtests of the DAS-II/Early Years: Verbal Comprehension, Picture Similarities, Naming Vocabulary, Pattern Construction, Matrices and Copying

Due to small sample size of ITT subjects who have been evaluated by the DAS-II Test for school age, the six core subtests for the DAS-II/School Age, including Recall of Designs, Word Definitions, Pattern Construction, Matrices, Verbal Similarities and Sequential and Quantitative Reasoning, cannot be analyzed using the MMRM model.

The estimated least squares means and 95% confidence intervals on the treatment comparison at Visit Weeks 16, 28, 40 and 52 from MMRM model will be presented in Forest plots for GCA score, standard scores for SNC and each of the three clusters (Verbal, Nonverbal, Spatial), and T scores for each of the six above-mentioned core subtests of the DAS-II/Early Years.

All other secondary efficacy endpoints listed above will be summarized descriptively by treatment group over time. When there is $>$ or \geq or $<$ or \leq recorded in the data, the inequality sign will be ignored for the age equivalents summary and the DQ calculation. DQ is defined as Age equivalent provided by the test $\times 100$ /Chronological age.

Mean observed values by treatment group will be plotted over time. This includes the following endpoints:

- The change from baseline to Visit Weeks 16, 28, 40, and 52 in the T scores, age equivalents and DQ for the core subtests of the DAS-II: Verbal Comprehension, Picture Similarities, Naming Vocabulary, Pattern Construction, Matrices and Copying for the DAS-II/Early Years; and Recall of Designs, Word Definitions, Pattern Construction, Matrices, Verbal Similarities and Sequential and Quantitative Reasoning for the DAS-II/School Years

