6.7.4 Subgroup Analyses

Subgroup analyses will be performed for the following subgroups:

- Baseline GCA classification groups. For this analysis, patients with a baseline GCA score of > 70 will be classified as having “Moderate” cognitive impairment, while patients with a baseline GCA score ≤ 70 will be classified as having “Severe” cognitive impairment. The randomization is stratified by this classification variable to ensure treatment group balance within these subgroups
- Baseline age group (either < 6 years or ≥ 6 years)
- Exploratory analysis for baseline age group (either < 55 months or ≥ 55 months).

Subgroup analyses are planned for the change from baseline in GCA and ABC standard scores, respectively. An MMRM model will be used to test for treatment by subgroup interactions. Interactions with a significance level of less than 10% will be considered potentially important and flagged for further clinical assessment. In general, the model will include fixed categorical effects for treatment, visit week, treatment by visit week interaction, subgroup, treatment by subgroup interaction, subgroup by visit interaction and the 3-way interaction between treatment, visit week and subgroup, and genotype. The p-values of interaction terms will be presented, as well as the least squares means and its 95% confidence intervals by treatment and visit for each subgroup classification factor. Descriptive statistics of the observed and change from baseline GCA and ABC standard scores will also be presented by treatment and visit week within each subgroup.

Additionally, the subgroup analysis will be performed for the age subgroup with baseline age < 6 years which may be the patient population with the most potential to benefit from the idursulfase-IT treatment. The change from baseline GCA score obtained at Visit Week 52 will be compared between the treatment groups using MMRM analysis. The repeated measures are the change from baseline GCA score obtained at the scheduled Visit Weeks 16, 28, 40, and 52, respectively. The model will include fixed categorical effects for treatment, visit week, treatment by visit week interaction, baseline GCA classification factor (either ≤ 70 or > 70), treatment by baseline GCA classification factor interaction, genotype and the baseline GCA score as a continuous covariate. Due to small sample size of ITT subjects with baseline age ≥ 6 years, MMRM model will not be applied for this age subgroup.

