9.2.1 Sample SAS code for the primary analysis

```
ods output estimates=est Tests3=FixF;
ods graphics on;
proc mixed data=adef data=adef covtest;
  class Trt VisitWk GCAclass Agegroup Genotype usubjid;
  model GCAchgBL = GCAclass Trt VisitWk Trt*Visitwk GCABL Agegroup Trt*GCAclass
  Trt*Agegroup GCAclass* Agegroup Genotype / ddfm=KR residual;
  repeated VisitWk / type=un subject=usubjid rcorr;
  estimate "Trt diff at Week 16" Trt 1 -1 Trt*VisitWk 1 0 0 0 -1 0 0 0 / cl;
  estimate "Trt diff at Week 28" Trt 1 -1 Trt*VisitWk 0 1 0 0 0 -1 0 0 / cl;
  estimate "Trt diff at Week 40" Trt 1 -1 Trt*VisitWk 0 0 1 0 0 0 -1 0 / cl;
  estimate "Trt diff at Week 52" Trt 1 -1 Trt*VisitWk 0 0 0 1 0 0 0 -1 / cl;
  lsmeans Trt*VisitWk / cl;
run;
```

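### The SAP adds treatment-by-age-group to the confirmatory models: patients aged 6 or over then count for half of the Week 52 contrast, which can become non-estimable without triggering the fallback

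*SAP*

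**What the plan says.** Protocol 10.5.1 specifies a primary MMRM with treatment, visit, treatment by visit, GCA class and baseline GCA. Protocol 10.5.2 uses the same form for ABC. Neither has an age term or any treatment-by-covariate interaction.

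SAP 6.7.1 adds age group (under 6, or 6 and over), treatment by GCA class and "treatment by baseline age group interaction, interaction between baseline GCA classification factor and baseline age group, genotype, and the baseline GCA score". SAP 6.7.2 adds "treatment by baseline age group interaction, interaction between baseline GCA classification factor and baseline age group, genotype, and the baseline ABC score". The endpoints in 6.7.3, which include the third gatekeeping family, are analysed "in the same manner as described above for the key secondary endpoint". SAP 7.2 declares the added interactions in one line and gives no reason.

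On inference, 6.7.1 says "Primary inference will be based on the treatment comparison of least squares means at Visit Week 52 from this model". The code in 9.2.1 tests Week 52 with the coefficients "Trt 1 -1 Trt*VisitWk 0 0 0 1 0 0 0 -1 / cl", listing none for treatment by age group, and requests LS-means without the observed-margins option. The code in 9.2.2 does likewise.

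SAP 6.7.1 foresees few older patients in an arm, and its remedy begins "If this model fails to converge, the treatment by baseline age group interaction and /or interaction". The only fallback in 6.7.2 is that "a first order autoregressive (AR(1)) covariance structure will be used instead". For the stand-alone analysis of patients aged 6 or over, 6.7.4 says "MMRM model will not be applied for this age subgroup".

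**The concern.** Three things go wrong once treatment by age group is in the model.

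- **Weighting.** Default LS-means average over the two age groups equally. The contrast matches the ITT mean difference in the stated hypothesis only if the effect is the same in both age groups. Half the coefficient rests on a group that the SAP itself considers too small for its own MMRM.
- **Estimability.** Randomisation is stratified by GCA class only, so one arm may contain no patient aged 6 or over. The contrast then does not exist, although the model can still be fitted.
- **Fallback.** The rule in 6.7.1 responds to non-convergence, which is a different event. Its and/or wording also leaves open which term goes. SAP 6.7.2 has no removal rule, and a change of covariance structure cannot restore a contrast that the design matrix does not support.

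The primary p-value opens the gatekeeping chain, so a failure here blocks everything below it. ANCOVA-WOCF (SAP 8.7) omits the interaction, but only as a sensitivity analysis.

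**Working it through.** **Inputs from SAP 4.2:** 48 patients, 32 IT and 16 control; effect 11, SD 11.6; key secondary effect 10, SD 10.5; 10% missing at Week 52; two-sided 5%. **From SAP 9.3.2:** SDs 3, 5, 8, 10 with AR(1) correlation 0.8, scaled by 11.6/10 = 1.16. **Assumed, because the documents do not say:** the number aged 6 or over (shown as IT+control), half the patients in each GCA class, and missing patients split 3 IT and 2 control.

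**1. The stated power.** With 29 and 14 evaluable, SE = 11.6 × √(1/29 + 1/14) = 3.775 and the noncentrality is 11/3.775 = 2.914. With 41 df, power is 81.2%. The key secondary gives 10.5 × √(1/29 + 1/14) = 3.417, 10/3.417 = 2.926 and power 81.5%. The stated 80% reproduces, for a two-sample t-test.

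**2. The coefficient.** In the over-parameterised design matrix, the contrast with literal zeros on treatment by age group is not estimable. The LS-means contrast carries +1/2, +1/2, −1/2, −1/2 on those four cells whatever the counts.

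**3. An empty cell.** With no control (or no IT patient) aged 6 or over, the design matrix loses one rank (18 to 17) and the contrast leaves its row space. The REML objective then equals that of the model without the interaction, so nothing impedes convergence. In 120 simulated trials with an empty control cell (4+0 and 6+0 older patients, 60 each), REML with unstructured covariance converged in 120. The contrast was estimable in none, with equal weights or observed margins.

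**4. Aliasing with both cells filled.** If all older IT patients are in one GCA class and all older controls in the other, the older group supplies two cell means for three parameters: age group, treatment by age group, and GCA class by age group. The contrast is again non-estimable.

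**5. How likely.** The chance of no older control among k older patients is C(32,k)/C(48,k). The other columns come from exact enumeration over treatment × GCA class × age cells with a rank check, without genotype.

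| k of 48 | no older control | no older IT | aliasing | total |
|---|---|---|---|---|
| 4 | 18.5% | 0.9% | 9.0% | 28.4% |
| 6 | 7.4% | 0.1% | 2.1% | 9.5% |
| 8 | 2.8% | 0.0% | 0.4% | 3.2% |

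A 12/20 and 6/10 split by GCA class gives 28.0%, 9.6% and 3.3%.

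**6. Power when the contrast is estimable.** GLS variance of the Week 52 contrast from four-visit design matrices, averaged over allocations with an estimable contrast (200 drawn per row), noncentral t, no genotype:

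| Older IT+control | SE | Primary | Key secondary |
|---|---|---|---|
| without the term | 3.64 | 84% | 84% |
| 2+1 | 4.21 | 72% | 72% |
| 3+1 | 4.15 | 73% | 74% |
| 4+2 | 3.90 | 78% | 79% |
| 6+3 | 3.76 | 81% | 81% |
| 8+4 | 3.70 | 83% | 83% |

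For the first row of older patients, 11/4.21 = 2.61 against 11/3.64 = 3.02 without the term. Observed ITT margins return primary power to 84% in every row. Adding treatment by GCA class alone costs nothing (83.8% both ways). Five random genotype levels lower these figures by about 1 to 2 points. Under flatter SDs of 9, 10, 11, 11.6, which are not from the documents, power without the term is 83%, against 36%, 39%, 54%, 67% and 75% with it.

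**7. Shift in the target.** With 4+2 older patients and no benefit in them, the expected contrast is 9.3 against an ITT difference of 9.6 (8.0 under the flatter SDs). The shift is small under the Appendix III covariance because there is no three-way term: the age interaction is held constant over visits and is estimated largely from the low-variance early ones.

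**The case against.** The strongest reply is that estimability depends only on counts of treatment, age and GCA class. The trial is open-label, and the sponsor has no access to unblinded scores during the study, so an empty or aliased cell can be found and handled before outcomes are compared. This stands: the change need not be outcome-driven. But the plan neither calls for that check nor says what follows from it.

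Second, when this SAP version was written the sponsor may have known its age counts, so the prospective odds may not describe the real position. That is fair, and the documents cannot settle it. SAP 6.7.1 nevertheless treats a low count in an arm as a live possibility.

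Third, 6.7.4 repeats the removal rule after describing refits of the primary and key secondary models, which suggests what was intended for 6.7.2. It governs subgroup and exploratory analyses and again depends on non-convergence, so it does not fill the gap.

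Fourth, equal-margin LS-means are conventional and SAP 7.2 discloses the added interactions. At 6+3 the SE (3.76) is no worse than that of the planning t-test (3.775), and under the Appendix III covariance the shift in target is about 0.3 points. All true. It limits the weighting and power arguments to small counts or a flatter covariance. It does not answer the fallback defect.

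**Conclusion.** The concern holds and should be fixed before the analysis. Certain, from the text and the algebra: the protocol has no such term; the coefficient is one half regardless of numbers; the contrast can be non-estimable in a converged model; and no written rule in 6.7.1 or 6.7.2 then applies. Appendix III, the SAP's support for the MMRM, simulated models without these interactions, so its finding of no convergence problems does not cover the planned model.

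Conditional on assumed counts: a 3.2% to 28.4% chance of a non-estimable contrast for 8 down to 4 older patients among 48. Where the contrast is estimable, power is below 80% at 4+2 or fewer under the scaled Appendix III covariance and little affected from 6+3 up. A flatter covariance would make the loss much larger, but the documents offer no support for one.

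**What to change.** Delete treatment by age group from the confirmatory models in SAP 6.7.1, 6.7.2 and 6.7.3 and from the code in 9.2.1 and 9.2.2. Keep age group as a main effect and leave the interaction test in 6.7.4. Treatment by GCA class and GCA class by age group need not go on power grounds.

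If the term is kept:

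1. Define the Week 52 contrast with observed ITT margins in both the LSMEANS and ESTIMATE statements.
2. Make the removal trigger either non-convergence or a non-estimable Week 52 contrast, and name the term to be removed. Observed margins alone do not cure an empty cell.
3. Write the same rule into 6.7.2, so that 6.7.3 inherits it.
4. Restate power for the final model.

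The cost is SAP wording and one model term in two code blocks. No new data are needed, and the age interaction is still tested.

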9.3.2 Simulation Methods

The baseline GCA score was generated as a normal random variable with a mean of 70 and standard deviation of 15 in both arms. An accept-reject approach was used to restrict the range of values to 55 to 85 (about 2/3 of the sample met this criterion). The records were divided into sets of 42 patients representing a clinical trial and randomly assigned to active or control groups in a 2:1 ratio using a Bernoulli distribution with parameter, $p = 2/3$. In this manner, approximately 3600 replications of a clinical trial dataset, each with 42 patients, were simulated.

In each replication, multivariate normal (MVN) data was generated for the repeated measures on the change in GCA score using SAS Proc SIMNORM with the following assumptions. Based on our Phase I/II data in the target population of interest, and under the alternative hypothesis, we assumed a 1 unit decline per month in GCA score in the untreated control arm. As up to 2 months may elapse between the baseline assessment and the start of idursulfase-IT treatment, a mean decline of 2 points at Month 13 would be expected if IT treatment was effective in stabilizing the decline. Therefore, under the alternative hypothesis the change in GCA data were generated assuming the following row vectors of mean changes and variances for the change from baseline corresponding to Months 4, 7, 10 and 13 in the control and active IT arms respectively:

Control: $\mu_c = (-4, -7, -10, -13)$, $\sigma^2 = (3^2, 5^2, 8^2, 10^2)$

Active: $\mu_a = (-2, -2, -2, -2)$, $\sigma^2 = (3^2, 5^2, 8^2, 10^2)$

This leads to the following row vector of mean treatment differences for the change from baseline (i.e. $\mu_a - \mu_c$): $\delta_a = (2, 5, 8, 11)$. The expected standard error of the mean difference at Month 13 is therefore $10(\sqrt{1/14+1/28})=3.3$. Similarly, under the null hypothesis of no treatment difference, MVN outcomes were generated with mean treatment differences $\delta_0 = (0, 0, 0, 0)$ with the same variances.

For each simulation, the data were generated using a first order auto-regressive (AR(1)) covariance structure with ij^{th} matrix element $\sigma_i\sigma_j\rho^{|i-j|}$, where the correlation between adjacent time points was set to $\rho = 0.80$. The covariance and correlation matrix was thus specified as displayed in [Tables A1](#) and [A2](#) respectively.

Table A1: Theoretical AR(1) Covariance Matrix for Repeated Measures (in change from baseline)				

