	Month 4	Month 7	Month 10	Month 13
Month 4	9.00	12.00	15.36	15.36
Month 7		25.00	32.00	32.00
Month 10			64.00	64.00
Month 13				100.00

Table A2: Theoretical AR(1) Correlation Matrix for Repeated Measures (in change from baseline)				
	Month 4	Month 7	Month 10	Month 13
Month 4	1.000	0.800	0.640	0.512
Month 7		1.000	0.800	0.640
Month 10			1.000	0.800
Month 13				1.000

The MMRM model included effects for treatment, month, treatment by month interaction and baseline GCA score as a continuous covariate. SAS Proc Mixed with restricted maximum likelihood estimation (REML) and an unstructured (UN) within-patient covariance structure was used. Note that a UN covariance structure was used in MMRM analyses even though an AR(1) structure was used to simulate the data, so as not to favor MMRM. The Kenward-Roger approximation was used to estimate denominator degrees of freedom. Similarly, the ANCOVA model for Month 13 contained effects for treatment and baseline GCA score as a continuous covariate. All scenarios were re-run adding a stratification factor for baseline GCA score (≤ 70 versus > 70) to each model. As the results for this set of simulations were nearly identical, results from the first set of simulations without the stratification factor are shown below. Power at Month 13, for the null and alternative hypothesis scenarios, was calculated for each analysis method using a 5% significance level.

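### The AR(1) fallback for the primary MMRM is not tied to a covariance matrix; read as the SAS option TYPE=AR(1), it understates the Week 52 standard error under the SAP's own variances

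*SAP*

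**What the plan says.** SAP 6.7.1 fits the MMRM in Proc Mixed with an unstructured covariance, REML and Kenward-Roger. Its fallback reads: "If this model fails to converge, a first order autoregressive (AR(1)) covariance structure will be used for the primary analysis". SAP 6.7.2 does the same for ABC: an "autoregressive (AR(1)) covariance structure will be used instead". SAP 6.7.3 extends that method to the cluster and domain scores, which "will be analyzed using a MMRM analysis in the same manner as described above for the key secondary endpoint". SAP 8.7 repeats the fallback and adds compound symmetric and Toeplitz structures as sensitivity analyses. Protocol 10.5.1, 10.5.2 and 10.8.6 use the same label. Sample code 9.2.1 and 9.2.2 shows only type=un.

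The label is spelled out only in SAP 9.3.2: "For each simulation, the data were generated using a first order auto-regressive (AR(1)) covariance structure with" element σᵢσⱼρ^|i−j|, SDs 3, 5, 8, 10 and ρ = 0.80. The same section adds: "Note that a UN covariance structure was used in MMRM analyses even though an AR(1) structure was used to simulate the data".

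SAP 6.7.1 then gives a second remedy. It warns that the "MMRM model may fail to converge when low count of subjects with baseline age" of 6 years or more exists in either arm, in which case "the treatment by baseline age group interaction and /or interaction between baseline GCA classification factor and baseline age group will be removed" from the model. SAP 6.7.2 contains the same interactions but has no removal step.

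**The concern.** The label has two readings. As a Proc Mixed option it means one common variance; as used in Appendix III it means a variance per visit. Two programmers could both follow the SAP and report different primary p-values.

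The choice matters because Week 52 is the only visit tested. If variability grows over time, a single variance averages the late visits with the less variable early ones, so the standard error that carries the inference is too small. Kenward-Roger adjusts within the assumed structure and does not correct a wrong one. The compound symmetric and Toeplitz checks named in 8.7 also assume equal variances in their standard form. The primary test opens the gate to the key secondary test and then to the six Family 3 tests, so an inflated primary test would undermine the strong familywise control claimed in 8.5.

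The second gap is the order of remedies. The plan does not say whether covariance or interactions change first, which interaction goes first, or whether the unstructured matrix is tried again after removal. That leaves the primary model open to choice after the data are seen.

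**Working it through.** **Inputs from the documents.** 48 patients, 32:16; difference 11; SD 11.6; 10% missing; two-sided 5% (SAP 4.2). Visit SDs 3, 5, 8, 10 and ρ = 0.80 (SAP 9.3.2). Model terms from SAP 6.7.1.

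**Assumed.** The genotype mix over five classes and the number aged 6 or over; neither is in the documents.

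**1. The plan's own figures.** Noncentral t power with 28.8 and 14.4 evaluable patients is 81.8%; with 28 and 14 it is 80.7%. The stated 80% reproduces. Table A1 follows exactly from σᵢσⱼρ^|i−j|: for Months 10 and 13, 8 × 10 × 0.8 = 64. So the matrix labelled AR(1) there is heterogeneous.

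**2. Large-sample effect of one variance.** Let S be Table A1 and V = σ²ρ^|i−j|. Minimising log|V| + tr(V⁻¹S) gives σ = 7.18 against a true Week 52 SD of 10. The ratio is 0.718, so the standard error is 28% too small. The type I error is 2Φ(−1.96 × 0.718) ≈ 15.9%.

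**3. The 6.7.1 model.** Null simulation with the inputs above, about 10% monotone dropout, REML and Kenward-Roger, and the Week 52 contrast weighted equally over GCA class and age group. Shortfall = 1 − (model SE ÷ empirical SD of the estimate). Set A: 2,000 trials per setting, up to three genotype mixes. Set B: 4,000 trials per setting, separately programmed.

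| Aged ≥6 (IT/control) | Set A: SE shortfall | Set A: type I error | Set B: SE shortfall | Set B: type I error |
|---|---|---|---|---|
| 2/1 | 5–6% | 6.4–6.8% | 4% | 6.2% |
| 4/2 | 9–14% | 7.4–9.8% | 12% | 8.6% |
| 6/3 | 19% | 10.9% | 19% | 11.2% |
| 8/4 | 21–25% | 11.9–13.7% | 20% | 11.7% |
| 12/6 | 25% | 14.4% | 26% | 13.8% |

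The shortfall shrinks with few older patients because the contrast then rests mainly on the treatment-by-age term. That term is constant over visits, and its standard error is not understated. In Set A, 460–510 of 2,000 trials at 2/1 and 39–53 at 4/2 had a non-estimable Week 52 difference and were excluded; no covariance choice cures those.

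**4. Which interaction is removed (TYPE=AR(1), Set A).**
- Both age interactions removed: shortfall 27–29%, type I error 14.8–16.0%.
- At 4/2, only GCA-class-by-age removed: 15% and 9.3%.
- At 4/2, only treatment-by-age removed: 27% and 14.6%.

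**5. Dependence on variance growth (4/2; interactions kept / both removed).**
- SDs 5, 7, 9, 11.6: type I error 8.5% / 14.3%.
- SDs 6, 7.5, 9, 10: 7.2% / 10.4%.
- Equal SDs: 5.2% / 4.5%.

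**6. Alternatives.** Heterogeneous AR(1) under the 6.7.1 model gives 4.4–5.9% (Set A) and 4.5–4.9% (Set B). Compound symmetry at 4/2 gives 8.3% with interactions kept and 15.7% with both removed.

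**7. Power for 11 points, SDs scaled to 11.6 at Week 52, same trials.** At 2/1: 48% with AR(1) against 72% with ARH(1). At 4/2: 72% against 78%.

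**8. Trigger.** The unstructured fit converged in all 353 estimable trials checked (not in SAS).

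**The case against.** The strongest reply is that these are error rates given that AR(1) is used, whereas the plan fits the unstructured model first. With 0 failures in 353, the 95% upper bound on the failure rate is 1 − 0.05^(1/353) ≈ 0.85%. Taking the 16% figure, overall error rises by at most about 0.0085 × 11 ≈ 0.1 percentage point, to about 5.1%. Appendix III also reports no convergence problems in about 3,600 simulated trials. In addition, the trigger the SAP names is a low count of older patients, which is where inflation is smallest, and the remedy it attaches to that warning is removing interactions. The variance growth is an assumption of a 42-patient methods simulation, not an observation. The Week 52 ANCOVA-WOCF and van Elteren analyses do not pool variance over visits, and the word introducing the extra structures in 8.7 leaves room for heterogeneous ones.

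Much of this stands. The operating error of the whole procedure is probably close to 5%, and the upper end of the range needs more older patients than the SAP suggests. However, Appendix III used a much smaller mean model, and the 353 fits rest on assumed data and were not run in SAS. A fallback is written for the case in which the first model fails, so it should be valid there. The sensitivity analyses might expose the problem, but they do not replace the p-value that carries inference.

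**Conclusion.** The concern holds, as something that should be fixed. The ambiguity and the missing order of remedies are plain from the text. If the fallback is used as TYPE=AR(1) and GCA variances grow as in Appendix III, the Week 52 confidence interval is too narrow and the primary test exceeds 5%: about 6–14% with the full 6.7.1 model for 3 to 18 patients aged 6 or over, and about 15–16% with both age interactions removed. With very few older patients and the interactions kept, inflation is small and the larger cost is power.

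The size rests on non-convergence occurring, on the Appendix III variances, and on assumed age and genotype mixes. With equal variances or the heterogeneous form there is no inflation. For ABC and the Family 3 endpoints the documents give no visit variances, so only the gap in wording is shown.

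**What to change.** Before database lock:

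- In SAP 6.7.1, 6.7.2 and 8.7, name the fallback as heterogeneous AR(1), TYPE=ARH(1), which is the matrix Appendix III already writes out. Show it in sample code 9.2.1 and 9.2.2. Align protocol 10.5.1, 10.5.2 and 10.8.6 at the next amendment.
- In SAP 6.7.1, state one fixed order for the two remedies, which interaction is removed first, and whether the unstructured covariance is tried again after removal. Say whether removal also applies in 6.7.2 and hence 6.7.3.
- As a clarification, add TYPE=CSH and TYPE=TOEPH to the structures listed in 8.7.

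The cost is a few lines of text and option names. The downside is up to three more variance parameters (four SDs instead of one), incurred only if the fallback is needed.
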